#### **10.3.3.2. Pharmacodynamic Statistical Inference**

The primary endpoint (SMR) will be analyzed using an analysis of covariance model (ANCOVA) to compare the effect of tirzepatide versus placebo. The dependent variable to be used in the model will be the change from baseline to 18 weeks in SMR. The independent variables will include treatment as a factor, baseline SMR and body composition parameter(s) as covariates. The primary analysis will be performed in all randomized subjects with evaluable data (modified intent-to-treat [mITT] population). Similar analysis will also be performed in subjects who reach the BW target range of  $-10\% (\pm 2\%)$  at Week 18 as a sensitivity analysis.

Other PD parameters that are scheduled to be measured only once postbaseline will be analyzed using a similar ANCOVA model with baseline measurement and treatment group as covariates. For parameters that are measured in the respiratory chamber, an adjustment for body composition parameter(s) as covariates may be applied if deemed appropriate. If the response is positive for all subjects and highly skewed, a log-transformation may be considered. Other parameters that are positive and skewed may be log-transformed.

The PD parameters that are scheduled to be measured at least twice postbaseline will be analyzed using a mixed-model repeated-measure method with restricted maximum likelihood estimation. The model will include the treatment, visit, and treatment-by-visit interaction as fixed effects, baseline value of the dependent variable as a covariate, and subject as a random effect. An unstructured variance-covariance matrix will be used to model the within-subject effects.

All PD analyses will be performed in the mITT population and selected analyses also on-BW-target population. All analyses will show least squares means of each treatment and the treatment difference in the original scale as well as standard error and 95% confidence interval. All tests will be done at the 2-sided 0.05  $\alpha$  level unless otherwise specified.

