Body weight was measured at baseline Day -1 (lead in) and multiple times post baseline. Plots of mean body weight and mean change from baseline values over time will be provided by treatment. The change from baseline to Day 8, Day 15, Day 22, Day 29, Day 36, Day 43, Day 50, Day 57, Day 64, Day 71, Day 78, Day 85, Day 92, Day 99, Day 106, Day 113, and Day 120-Day 125 (average of nonmissing measurements at Days 120, 123, 124, 125 used) will be analyzed using a mixed-model repeated measures (MMRM) method with restricted maximum likelihood (REML) estimation.

- > Independent variables: treatment, time, and treatment-by-time interaction as fixed effects, baseline body weight as a covariate, and patient as a random effect
- Response variable: change from baseline in body weight

An unstructured covariance structure will be used to model the relationship of within-subject errors. If this model fails to converge, the following variance covariance structures will be tested in order until convergence is achieved:

- heterogeneous Toeplitz
- heterogeneous first order autoregressive
- heterogeneous compound symmetry
- Toeplitz
- first order autoregressive, and
- compound symmetry.

The first covariance structure that converges will be used.

- change from baseline to Week 18 in
 - o body fat-free mass (kg)
 - o body fat mass (kg)
 - o percentage of body fat mass (total region % of fat)

Note: DXA scan parameters: DXA Weight and DXA Region Fat (%) will be provided in datasets to statisticians. Fat mass and fat free mass will be calculated for 2 DXA scans on the same day:

• Fat Mass = DXA Region Fat (%)/100 * DXA Weight

• Fat Free Mass = DXA Weight – Fat Mass

The mean value of nonmissing measurements from the 2 DXA scans on the same day will be calculated for analyses.

The above body composition parameters will be analyzed using ANCOVA to compare the effect of tirzepatide versus placebo:

- Independent variables: treatment as a factor, baseline body composition parameter as a covariate
- Response variable: change from baseline to Week 18 in body composition parameter.

Lipid Metabolism

Secondary PD measures to assess the effect of tirzepatide 15 mg versus placebo on parameters of lipid metabolism:

- change from baseline to Week 18 in lipid metabolism measurements during sMMTT in:
 - triglycerides
 - o cholesterol
 - o LDL cholesterol
 - VLDL cholesterol
 - HDL cholesterol
 - o FFA
 - o glycerol
 - o 3-hydroxybutyrate (ie beta-hydroxybutyrate)
 - o acylcarnitines

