All the above lipid metabolism lab measurements will be calculated for (1) fasting; (2) total AUC_{0-4hr} ; (3) incremental AUC_{0-4hr} for analyses.

Note: For fasting measurements, it is collected on Day -4 (lead in, 10 minutes prior to sMMTT), Day 29 (Week 5), Day 57 (Week 9), Day 122 (Week 18; 10 minutes prior to sMMTT). For AUC parameters, it is derived for baseline and Week 18 during sMMTT.

Note: See Section 6.9.1 for AUC calculation details. All these fasting lab measurements and AUCs will be reported in both International System of Units (SI Units) and conventional units.

- change from baseline to Week 18 in lab measurements during sMMTT of:
 - o ApoB-48
 - o ApoB-100
 - o ApoC-III
 - o LPL

All the above lipid metabolism lab measurements will be calculated for (1) fasting; (2) total AUC_{0-4hr}; (3) incremental AUC_{0-4hr} for analyses.

Note: For fasting measurements, it is collected Day -4 (lead in, 10 minutes prior to sMMTT), Day 29 (Week 5), Day 57 (Week 9), Day 122 (Week 18; 10 minutes prior to sMMTT). For AUC parameters, it is derived for baseline and Week 18 during sMMTT.

Note: See Section 6.9.1 for AUC calculation details. All these fasting lab measurements and AUCs will be reported in both SI Units and conventional units.

The above available laboratory fasting parameters will be analyzed in a manner similar to the secondary PD analysis on body weight using MMRM to compare the effect of tirzepatide versus placebo.

- ➤ Independent variables: treatment, time, and treatment-by-time interaction as fixed effects, baseline as a covariate, and patient as a random effect
- Response variable: change from baseline

The above available laboratory AUC parameters during sMMTT will be analyzed using ANCOVA to compare the effect of tirzepatide versus placebo:

- ➤ Independent variables: treatment as a factor, baseline as a covariate
- Response variable: change from baseline to Week 18.

Time profile plots of the lab measurements (mean \pm standard deviation) during sMMTT (over 6 time points) will be provided by treatment for baseline and Week 18.

- change from baseline through Week 18 in fasting concentration of:
 - o leptin
 - o adiponectin
 - o IGFBP 1
 - o IGFBP 2

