For HbA1c, it is scheduled to be measured at baseline (Day -4) and twice postbaseline (Day 57 [Week 9] and Day 122 [Week 18]). It will be analyzed in a similar manner to secondary PD analysis on body weight using MMRM:

- ➤ Independent variables: treatment, time, and treatment-by-time interaction as fixed effects, baseline HbA1c as a covariate, and patient as a random effect
- Response variable: change from baseline in HbA1c

Note: HbA1c will be reported in % and mmol/mol, where

$$HbA1c (mmol/mol) = 10.93 \times HbA1c (\%) - 23.5$$

Inferential statistics includes LS means and standard error of the measure for each treatment (tirzepatide, placebo), and the estimated treatment difference (tirzepatide - placebo), corresponding 2-sided 95% CI, and associated p-value.

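### Every MMRM adds a patient random effect to an unstructured error matrix: one parameter too many, which can make the SAP's convergence rule discard the unstructured model for no real reason

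*SAP*

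**What the plan says.** SAP 6.9.2.2 models change in body weight with treatment, time and their interaction as fixed effects, and "baseline body weight as a covariate, and patient as a random effect". It then states: "An unstructured covariance structure will be used to model the relationship of within-subject errors". The analysed time points are Days 8 to 113 weekly, ending with "Day 106, Day 113, and Day 120-Day 125 (average of nonmissing measurements at Days 120, 123, 124, 125 used".

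The fallback rule reads: "If this model fails to converge, the following variance covariance structures will be tested in order until convergence is achieved". The order is heterogeneous Toeplitz, heterogeneous AR(1), heterogeneous compound symmetry, Toeplitz, AR(1), compound symmetry. The section closes: "The first covariance structure that converges will be used".

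The other MMRMs are to be run in a manner similar to body weight and repeat the random effect:

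- fasting lipids, and leptin, adiponectin, IGFBP 1 and 2: "baseline as a covariate, and patient as a random effect";
- HbA1c: "baseline HbA1c as a covariate, and patient as a random effect";
- FCI and FPQ (SAP 6.9.2.3): the same, with the baseline questionnaire parameter as covariate.

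Protocol 10.3.3.2 has "baseline value of the dependent variable as a covariate, and subject as a random effect" together with an unstructured matrix, and the protocol synopsis repeats it. The SAP does not say whether the random effect stays in the fallback models, or whether a singular Hessian or a zero variance estimate counts as non-convergence.

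**The concern.** An unstructured matrix already holds every variance and covariance among the visits. A random intercept adds the same constant to all of them, so the likelihood cannot divide that constant between the two components. Software may then report a singular fit or fail to converge.

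The written rule reacts to non-convergence by changing the covariance model, and chooses the replacement by convergence alone. The reported model for a secondary or exploratory endpoint could therefore depend on how the software handles a redundancy that the plan itself created. The last three structures on the list force equal variances at all visits. If the variance of change grows over time, such a structure understates the standard error at Week 18, the visit of interest.

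**Working it through.** **The plan's own figure.** No figure is stated for any MMRM. The only design figure is at least 80% power for SMR. With 46 completers (23 per arm), a difference of 100 kcal/day, SD 117 and two-sided 0.05, the t-test power is 80.9%. It reproduces and does not bear on this point.

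**Inputs.** Post-baseline time points T, from SAP 6.9.2.2 and 6.9.2.3:
- body weight: 16 weekly visits plus the Day 120 to 125 average, T = 17;
- fasting lipids, leptin, adiponectin, IGFBP 1 and 2: Days 29, 57 and 122, T = 3;
- HbA1c (Days 57 and 122), FCI and FPQ (Days 50 and 123): T = 2.

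The SAP gives no structure for the random effect; a random intercept with variance σ_b² is assumed.

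**Step 1: parameter count.** The marginal covariance is V = σ_b²J + R, where J is a matrix of ones. V has T(T+1)/2 distinct elements. With R unstructured, (σ_b² + c, R − cJ) gives the same V for a range of c.

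| T | Elements of V | Parameters with random intercept | Rank |
|---|---|---|---|
| 17 | 17×18/2 = 153 | 154 | 153 |
| 3 | 3×4/2 = 6 | 7 | 6 |
| 2 | 2×3/2 = 3 | 4 | 3 |

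**Step 2: the fallback list with the random intercept kept** (numerical rank of the map from parameters to V).

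| Structure | T = 17 | T = 3 | T = 2 |
|---|---|---|---|
| Heterogeneous Toeplitz, AR(1), CS | identifiable | identifiable | not identifiable |
| Toeplitz | not identifiable | not identifiable | not identifiable |
| AR(1) | identifiable | identifiable | not identifiable |
| CS | not identifiable | not identifiable | not identifiable |

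At T = 2 the three heterogeneous structures each have two variances and one correlation, so they are the unstructured model in another form.

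**Step 3: does redundancy alone change the result?** In a simulated example (46 subjects, T = 3), σ_b² was moved from 0 to 3.3 along the flat direction. The −2 REML log-likelihood stayed at 320.33 and the Week 18 standard error at 1.048. It does not.

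**Step 4: what if body weight reached an equal-variance structure?** The documents give no SDs of weight change by visit. Assume that the SD rises linearly over 17 visits. Compound symmetry then uses the pooled SD, the root mean square of the visit SDs. The ratio of model to true standard error is r = pooled SD / Week 18 SD, and the type I error is 2(1 − Φ(1.96r)).

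| SD, Day 8 to Week 18 (kg) | Pooled SD | r | Type I error |
|---|---|---|---|
| 5 to 5 | 5.00 | 1.00 | 5% |
| 3 to 5 | 4.05 | 0.81 | 11% |
| 2 to 5 | 3.62 | 0.72 | 16% |
| 1 to 5 | 3.24 | 0.65 | 20% |

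Toeplitz and AR(1), fitted to the same SDs with assumed lag-1 correlation 0.90 to 0.97, give 0.81 to 0.82, 0.74 to 0.75 and 0.67 to 0.71 for the last three rows.

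**Step 5: the heterogeneous fallbacks for body weight.** Under that AR-type correlation, heterogeneous AR(1) gives 1.00, heterogeneous CS gives 1.05 to 1.08 (slightly conservative), and heterogeneous Toeplitz gives 1.00 by construction. They are not safe in every case. If weight change instead follows an assumed random-slope or Brownian pattern, heterogeneous Toeplitz and AR(1), fitted without the random intercept, give about 0.74 to 0.81.

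**The case against.** The strongest reply is that the redundancy is harmless and the path to harm is long. Step 3 supports the first half: an accepted fit gives the right estimate and standard error. At 3 and 17 visits the three structures tried next have visit-specific variances and are identifiable. An equal-variance structure is reached only if all three also fail, and the random intercept does not make them unidentifiable. At 2 visits, a rule that rejected singular fits consistently would reject all seven structures, while one that accepted them would use the unstructured model. These limits stand. They leave a rule whose outcome at 2 visits is undefined, and a route at every T by which the unstructured model is dropped without cause.

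The phrase may also be meant only to name the subject as the clustering unit. That is possible, but it stands in the list of model effects in every MMRM, and a programmer could well fit it.

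Nor does deletion guarantee convergence: 153 covariance parameters remain for body weight with about 46 completers. A fallback used then would answer a real difficulty.

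A reader might infer that confidence intervals and p-values for HbA1c, lipids, FCI and FPQ are also wrong by the amounts in Step 4. The documents do not support that. The figures rest on assumed growth in the spread of weight change, which says nothing about those endpoints. For weight itself the documents report no such growth, and both arms are steered to an 8% to 12% loss and then to maintenance.

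**Conclusion.** The specification is wrong as written: read as a random intercept, the patient effect makes every MMRM over-parameterised by exactly one parameter, whatever the sample size. The practical consequence is conditional. Nothing changes if the fit is accepted. If it is treated as non-converged, the preferred model is lost for an artificial reason, and for HbA1c, FCI and FPQ no listed structure is identifiable while the random effect is kept.

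For the Week 18 weight standard error, the effect ranges from none, if the chosen structure fits, to a ratio of about 0.65 to 0.82 and a type I error of about 11% to 20%. The latter needs both an equal-variance structure and SD growth to 5 kg from 1 to 3 kg. Only secondary and exploratory MMRMs are touched; the primary SMR analysis is an ANCOVA.

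**What to change.** Delete patient or subject as a random effect from every MMRM in SAP 6.9.2.2 and 6.9.2.3, and from the protocol synopsis and Section 10.3.3.2. Use subject only to index the unstructured repeated error matrix, and state that the same holds for each fallback structure. Where both versions converge, results are identical, so nothing is lost.

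Two additions are optional. Define convergence to include a positive-definite Hessian. Allow an equal-variance structure only with a robust standard error that has a small-sample correction; with about 23 completers per arm, making robust errors mandatory is debatable.

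The cost is a few lines of SAP text and one line of code per model. SAP 6.2 requires a protocol amendment only when a principal feature changes. Otherwise the change can be recorded in SAP Section 8 and the protocol wording aligned when it is next revised.

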## Study Schedule Protocol I8F-MC-GPGU: Treatment Period

Procedure	Treatment															Comments
Visit	3	4	5	6	7	8	9	10	11	12	13	14	15	16	17	
Week of Treatment	1	2	3	4	5	6	7	8	9	10	11	12	13	14	15	
Study Day	1	8 ±1	15 ±1	22 ±1	29 ±1	36 ±1	43 ±1	50 ±1	57 ±1	64 ±1	71 ±1	78 ±1	85 ±1	92 ±1	99 ±1	
Clinical Procedures																
Weight		P	P	P	P	P	P	P	P	P	P	P	P	P	P	Refer to screening and lead-in table.
Vital signs (BP/PR/body temperature)		P	P	P	P		P		P				P			Refer to screening and lead-in table.
ECGs									X							Refer to screening and lead-in table.
Concomitant medications	X	X	X	X	X	X	X	X	X	X	X	X	X	X	X	
AEs	X	X	X	X	X	X	X	X	X	X	X	X	X	X	X	
Physical examination/medical assessment							X									Refer to screening and lead-in table.
CRU discharge	X															CRU discharge will be ± 1 day.
C-SSRS (Since Last Visit Version) + SHSF + SHFF				X				X				X				The SHFF is required only if triggered by the SHSF, per instructions in the form. The C-SSRS since last visit version here refers to when last C-SSRS assessment was performed.
PHQ-9								X								
Outpatient		X	X	X	X	X	X	X	X	X	X	X	X	X	X	
Investigational Product																
Investigational product administration	X	X	X	X	X	X	X	X	X	X	X	X	X	X	X	
Laboratory Tests																
Safety laboratory tests (including hemoglobin A1c and calcitonin)									X							
Glucose					X											Fasting sample.
Insulin, leptin, adiponectin, IGFBP 1, IGFBP 2					X				X							Fasting samples.

Procedure	Treatment															Comments
Visit	3	4	5	6	7	8	9	10	11	12	13	14	15	16	17	
Week of Treatment	1	2	3	4	5	6	7	8	9	10	11	12	13	14	15	
Study Day	1	8	15	22	29	36	43	50	57	64	71	78	85	92	99	
Lipid panel: • Triglycerides, total cholesterol • LDL-C, VLDL-C, HDL-C • ApoB-48, ApoB-100, ApoC-III • LPL FFA, glycerol, acylcarnitine 3-hydroxybutyrate				P					P							Fasting samples.
Investigative Tests																
Retrospective VAS	X	X	X	X	X	X	X	X	X	X	X	X	X	X	X	
Food craving inventory and food preference questionnaire								X								
Diagnostics																
PK sample	P			P				P								All samples for PK and immunogenicity must be taken predose, and time-matched as much as possible.
Immunogenicity	P			P				P								
Nonpharmacogenetic stored samples	P			P				P								Fasting samples.
Pharmacogenetic sample	P															

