### Safety Laboratory Tests

Hematology	Clinical Chemistry
Hematocrit	Sodium
Hemoglobin	Potassium
Erythrocyte count (RBC)	Bicarbonate
Mean cell volume	Chloride
Mean cell hemoglobin	Calcium
Mean cell hemoglobin concentration	Phosphorus
Leukocytes (WBC)	Glucose (fasting)
Absolute counts of:	Blood urea nitrogen
Neutrophils	Uric acid
Lymphocytes	Total protein
Monocytes	Albumin
Eosinophils	Total bilirubin
Basophils	Alkaline phosphatase
Platelets	Alanine aminotransferase
	Aspartate aminotransferase
	Creatinine
	Lipase (fasting)
	Amylase
Urinalysis	Triglyceride b
Specific gravity	Total cholesterol b
pH	Hemoglobin A1c
Protein	
Glucose	
Ketones	
Bilirubin	
Urobilinogen	
Blood	
Leukocytes	
Microscopy a	
	Endocrine
	Follicle-stimulating hormone a
	Calcitonin
	Serologyc
	Hepatitis B surface antigen
	Hepatitis C antibody, hepatitis C RNA d
	HIV antibody
	Pregnancy test (urine, serum) e
	Drug and alcohol screen f

Abbreviations: HIV = human immunodeficiency virus; RBC = red blood cells; WBC = white blood cells.

Note: Results of these assays will be validated by the central or local laboratory at the time of testing. Additional tests may be performed or auto-calculated by the laboratory as part of its standard panel that cannot be removed. Some of the above parameters are calculated from measured values. Omission of calculated values will not be considered as a protocol violation.

a If clinically indicated, per investigator's discretion.

b Triglyceride and total cholesterol concentrations in the safety panel will not be required on the days that the lipid panel is performed.

c At screening only (unless previously performed within the last 6 months with reports available for review).

d See exclusion criteria (Section 6.2) for further details.

- e Pregnancy tests will be performed for women of childbearing potential. Serum pregnancy test is done at screening and follow-up and urine pregnancy is performed on Day -4 and Day 122.
- f Performed at screening. Procedures may be repeated throughout the study as deemed necessary by the investigator.

---

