**Protocol I8F-MC-GPGU Sampling Summary**

Purpose	Blood Volume per Sample (mL)	Number of Blood Samples	Total Volume (mL)
Screening tests a,b	24	1	24
Safety laboratory tests (including hemoglobin A1c and calcitonin) a,b	15	5	75
Tirzepatide pharmacokinetics c	3	5 (+3)	24
Pharmacodynamics c			
3-hydroxybutyrate (fasted)	2	2	4
3-hydroxybutyrate (fasted) during sMMTT	2	6 × 2	24
Acylcarnitine (fasted)	5	2	10
Acylcarnitine (fasted) during sMMTT	5	6 × 2	60
Adiponectin (fasted)	2	2	4
Adiponectin (fasted) during sMMTT	2	1 × 2	4
Free fatty acid (fasted)	2	2	4
Free fatty acid (fasted) during sMMTT	2	6 × 2	24
Glucose (fasted)	2	2	4
Glucose (fasted) during sMMTT	2	11 × 2	44
Glycerol	2	2	4
Glycerol during sMMTT	2	6 × 2	24
IGFBP 1 and 2 (fasted)	5	2	10
IGFBP 1 and 2 (fasted) during sMMTT	5	1 × 2	10
Insulin (fasted)	2.5	2	5
Insulin (fasted) during sMMTT	2.5	9 × 2	45
Leptin (fasted)	2	2	4
Leptin (fasted) during sMMTT	2	1 × 2	4
Lipid panel (fasted): TG, total cholesterol, LDL-C, VLDL-C, HDL-C	7.5	2	15
Lipid panel (fasted): TG, total cholesterol, LDL-C, VLDL-C, HDL-C during sMMTT	7.5	6 × 2	90
Lipid panel (fasted): ApoB-48, ApoB-100, ApoC-III	3.5	2	7
Lipid panel (fasted): ApoB-48, ApoB-100, ApoC-III during sMMTT	3.5	6 × 2	42
Lipid panel: LPL	2.5	2	5
Lipid panel: LPL during sMMTT	2.5	6 × 2	30
OGTT at screening – glucose (2 mL) and Insulin (2.5 mL) b	4.5	2	9

continued

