$$p_1 = 289, p_2 = 270, p_3 = 14,000, p_4 = 440, p_5 = 0.000637, p_6 = 117$$

 D_0 is an oral glucose dose (expressed in grams per square meter)

(D₀ = carbohydrate intake [gram] during sMMTT / BSA [m²], where Gehan and George body surface area formula is BSA=0.1640443958298 × weight[kg]^{0.515} × (height[cm]/100)^{0.422} [Bailey and Briars 1996])

V=10,000 mL/m² (the total glucose distribution volume)

$$G_{CLAMP} = 90 \text{ mg/dL}$$

 $G_0 = \text{glucose concentration (mg/dL) at 0 minute (fasting)}.$

 I_0 = insulin concentration ($\mu U/mL$) at 0 minute (fasting).

 G_{120min} = glucose concentration (mg/dL) at 120 min

 I_{120min} = insulin concentration ($\mu U/mL$) at 120 min

 G_{180min} = glucose concentration (mg/dL) at 180 min

Note: Fasting measurement will be the mean of non-missing measurements at -10 and -1 minutes of sMMTT.

Stumvoll Index (Stumvoll et al. 2000; Stumvoll et al. 2001)
 Stumvoll ISI = 0.222 - 0.00333 BMI - 0.0000779 I_{120min} - 0.000422 Age

Where I_{120min} = insulin concentration (pmol/L) at 120 min

The above insulin sensitivity parameters during sMMTT will be analyzed using ANCOVA to compare the effect of tirzepatide versus placebo:

- ➤ Independent variables: treatment as a factor, baseline as a covariate
- Response variable: change from baseline to Week 18.

Glucose Control

Secondary PD measures to assess the effect of tirzepatide 15 mg versus placebo on parameters of glucose control:

- change from baseline to Week 18 in fasting and postmeal serum glucose during sMMTT
 - fasting glucose
 - mean of nonmissing glucose measurements at -10 and -1 minutes of sMMTT
 - o total glucose AUC_{0-4hr}
 - o incremental glucose AUC_{0-4hr}

Note: See Section 6.9.1 for AUC calculation details. All these glucose parameters will be reported in the SI Units and conventional units.

The above glucose parameters during sMMTT will be analyzed using ANCOVA to compare the effect of tirzepatide versus placebo:

- Independent variables: treatment as a factor, baseline as a covariate
- Response variable: change from baseline to Week 18.

Time profile plots of serum glucose levels (mean \pm SD) during sMMTT (over 11 time points) will be provided by treatment for baseline and Week 18.

• change from baseline through Week 18 in HbA1c

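### Fasting glucose and HOMA2-IR are tested at Week 18 only, although earlier fasting samples are scheduled and the SAP uses the same visits in an MMRM for fasting lipids and leptin

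*SAP*

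**What the plan says.** **Protocol rule.** Section 10.3.3.2 assigns the model by the number of scheduled measurements. For two or more: "The PD parameters that are scheduled to be measured at least twice postbaseline will be analyzed using a mixed-model repeated-measure method". For one: "Other PD parameters that are scheduled to be measured only once postbaseline will be analyzed using a similar ANCOVA model".

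**Samples.** The treatment-period Schedule of Activities has one row for "Insulin, leptin, adiponectin, IGFBP 1, IGFBP 2", marked at Weeks 5 and 9 as fasting samples. Glucose has its own row with a single mark, at Week 5. The Week 9 safety panel contains fasting glucose (Appendix 2). Appendix 5 counts, under pharmacodynamics and apart from the sMMTT, two fasted glucose and two fasted insulin samples.

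**SAP.** Section 6.9.1 lists Day 29 and Day 57 fasting values for the lipid panel, 3-hydroxybutyrate, acylcarnitines, FFA, glycerol, leptin, adiponectin and IGFBP 1 and 2. Glucose and insulin are not on that list. Section 6.9.2.2 builds HOMA2-IR and fasting glucose from the samples 10 minutes and 1 minute before the test meal, and tests change to Week 18: "The above insulin sensitivity parameters during sMMTT will be analyzed using ANCOVA to compare the effect of tirzepatide versus placebo" and "The above glucose parameters during sMMTT will be analyzed using ANCOVA to compare the effect of tirzepatide versus placebo". Fasting lipids, leptin, adiponectin, IGFBP and HbA1c are analysed by MMRM. Section 8 lists four changes from the protocol, and this is not one of them.

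**The concern.** Two secondary endpoints are handled differently from their closest neighbours, with no reason given. The sMMTT takes place only at baseline and Week 18. Subjects who stop investigational product are also withdrawn from the study (protocol 8.1.1), and the SAP states no imputation. The Week 18 ANCOVA therefore rests in effect on subjects who reach the Week 18 sMMTT, although the defined analysis set is all evaluable PD data from dosed randomised subjects.

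A subject who leaves after Week 5 or Week 9 has given fasting blood that could inform the Week 18 comparison, and the SAP does not use it. At stake are a little precision and, if leaving is related to early response, some bias.

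**Working it through.** **1. Check of the sample count.** Appendix 5 gives glucose 2 × 2 mL = 4 mL and insulin 2 × 2.5 mL = 5 mL outside the sMMTT. Adding all lines of the table gives 754 mL, the stated total, so these samples are in the blood budget.

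**2. Scheduled postbaseline fasting values.**

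| Parameter | Week 5 | Week 9 | Week 18 | Count | SAP model |
|---|---|---|---|---|---|
| Leptin, adiponectin, IGFBP | yes | yes | yes | 3 | MMRM |
| Fasting lipids (endpoint worded as sMMTT) | yes | yes | yes | 3 | MMRM |
| Fasting insulin | yes | yes | yes | 3 | no model of its own |
| Fasting glucose | yes | safety panel, or second Appendix 5 sample | yes | 2 or 3 | ANCOVA |
| HOMA2-IR | derivable | if glucose is available | yes | 2 or 3 | ANCOVA |

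If the parameter is the fasting analyte, glucose and HOMA2-IR reach the protocol's threshold of two, even without Week 9. If the parameter is the sMMTT value, the count is 1 and ANCOVA is what the protocol prescribes.

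**3. Subjects affected.** 56 × 0.15 = 8.4 expected to leave, so 56 − 8.4 = 47.6 remain. The plan's own target of about 46 completers implies 56 − 46 = 10. So about 8 to 10 of 56 have no Week 18 value.

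**4. Size of the gain.** The documents give no SD, between-visit correlation or dropout pattern for these endpoints, so the following is illustrative. Common settings: 28 per arm, three postbaseline visits, unit SD, about 15% dropout, 4000 replicates. A likelihood analysis using Weeks 5 and 9 stands in for the MMRM.

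*Random dropout.* Both analyses are unbiased. With a true effect of −0.50 SD, the variance ratio (likelihood to ANCOVA) is 0.971, 0.933 and 0.904 at correlations 0.4, 0.6 and 0.8. The reduction in SE is 1 − √ratio: 1.5%, 3.4% and 4.9%. A second set, with a true effect of −0.7 SD, gave SEs of 0.275 against 0.282 at correlation 0.5 (1 − 0.275/0.282 = 2.5%) and 0.276 against 0.288 at 0.7 (4.2%). A further run gave 1 to 2%.

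*Active-arm dropout concentrated in those with the largest early fall, all leaving after Week 9.* Against a true −0.50:

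| Correlation | Week 18 ANCOVA | Bias | Likelihood with Weeks 5 and 9 |
|---|---|---|---|
| 0.4 | −0.394 | 0.11 | −0.502 |
| 0.6 | −0.344 | 0.16 | −0.506 |
| 0.8 | −0.278 | 0.22 | −0.492 |

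Other assumed dropout models gave smaller ANCOVA biases: 0.12 and 0.16 SD in one set, 0.07 to 0.09 SD in another. The size depends on the assumed link.

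*When the subjects leave.* Active-arm dropout tied to the Week 9 value, correlations 0.5 and 0.7:

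| Timing of departure | Bias with earlier visits used (SD) |
|---|---|
| All after Week 9 | about 0.00 (ANCOVA 0.09 and 0.13) |
| Half before Day 29 | 0.04 and 0.06 |
| All before Day 29 | 0.10 and 0.14, no correction |

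An independent re-run with similar settings showed the same pattern: full, about half, and no correction.

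**The case against.** The strongest reply is that the SAP follows the protocol. Both endpoints are defined as measured during the sMMTT, which is done once after baseline, and protocol 9.1 places the planned efficacy assessments at baseline and end of treatment. On that reading the ANCOVA rule applies and Section 8 has nothing to declare. Leptin and its companions differ because their endpoint is simply a fasting concentration. This stands as a reading of the protocol, so a clear breach of 10.3.3.2, which a reader might infer, is not established. It does not explain the lipids: they carry the same sMMTT wording, yet the SAP splits them into fasting values (MMRM) and AUCs (ANCOVA).

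Other points that stand:
- A reader might infer that the early samples are used nowhere. SAP 6.9.2 provides for summaries of postbaseline PD values, and 6.10.8 summarises clinical chemistry by visit, so only inferential use is missing.
- Week 9 glucose is not marked in its own row. If it comes from the safety panel, Appendix 5 places that test on site or in a local laboratory and the PD assays in a central or referral laboratory. It would also be one draw, where the SAP averages two.
- A reader might infer that an MMRM removes dropout bias. Dose escalation fills Weeks 1 to 8, so subjects who leave during it may have neither sample, or only the Week 5 one. The documents also do not link dropout to fasting glucose or insulin in these non-diabetic subjects.
- Fasting insulin is not a listed endpoint, and the stated objective is the effect at 18 weeks, so the early time course is a by-product.

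**Conclusion.** The point holds as an unexplained inconsistency within the SAP. Scheduled fasting insulin and glucose at the early visits enter no inferential analysis, while fasting lipids and the analytes in insulin's own schedule row do. The consequence is modest: about 1 to 4% in SE under random dropout at correlations up to 0.7, and just under 5% at 0.8. If active-arm dropout follows early response, the Week 18 ANCOVA was biased by about 0.07 to 0.22 SD across the assumed models. The MMRM reduces that bias only for subjects who have a Week 5 or Week 9 sample, and not at all for those who leave before Day 29. All these figures rest on assumed correlations and dropout models. Two of many secondary endpoints are involved; the primary SMR analysis and its power are untouched. The change is worth making because it is nearly free.

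**What to change.** 1. Reconcile the single glucose mark in the treatment-period schedule with the two fasted glucose samples in Appendix 5, and state the source of any Week 9 glucose. If only a safety-panel value exists, record the possible laboratory difference and the single draw.
2. In SAP 6.9.1, add fasting insulin and glucose at Day 29 and Day 57 to the list of fasting samples, and say at which visits HOMA2-IR is derived.
3. In SAP 6.9.2.2, analyse fasting glucose and HOMA2-IR with the MMRM already written for fasting lipids. Keep the Week 18 contrast as the endpoint, and keep ANCOVA for the AUCs, Matsuda, OGIS and Stumvoll. An MMRM for fasting insulin is optional.
4. If the sponsor prefers the sMMTT-only reading, state it with its reason in Section 8, including why the lipids are treated differently.

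Cost: SAP wording, a few more model runs and the schedule reconciliation. No blood beyond what Appendix 5 already budgets is needed.
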